6.2.1.1 Permitted concomitant therapy requiring caution and/or action

HMG-CoA Reductase Inhibitors (statins)

Patients will be permitted to use HMG-CoA reductase (3-hydroxy-3-methyl-glutaryl-CoA) inhibitors during the study, but these drugs should be used with caution and a 50% dose reduction of the HMG-CoA reductase inhibitor is recommended, with close monitoring for safety, such as liver chemistry and signs and symptoms of myolysis, and efficacy, such as cholesterol and triglycerides (refer to individual product information for monitoring recommendations).

Polyvalent Cations (Chelation)

Eltrombopag chelates with polyvalent cations such as aluminum, calcium, iron, magnesium, selenium and zinc. Eltrombopag should be taken at least two hours before or four hours after

any products such as antacids, dairy products, or mineral supplements containing polyvalent cations to avoid significant reduction in eltrombopag absorption.

Food Interaction

To avoid significant reduction in eltrombopag absorption, eltrombopag should be taken at least two hours before or four hours after food containing > 50 mg calcium and at least one hour before to two hours after food containing little (< 50 mg) (or preferably no) calcium. The administration of a single 50 mg dose of eltrombopag with a standard high-calorie, high-fat breakfast that included dairy products led to reduced eltrombopag exposure. Foods low in calcium (defined as < 50 mg calcium per serving) including fruit, lean ham, beef and unfortified (no added calcium, magnesium, iron) fruit juice, unfortified soy milk, and unfortified grain did not significantly impact plasma eltrombopag exposure, regardless of calorie and fat content.

Substrates of OATP1B1 or BCRP

Concomitant administration of eltrombopag and other OATP1B1 or BCRP substrates should be undertaken with caution.

Examples of drugs which are OATP1B1 or BCRP substrates are given in [Appendix 16.1](#).

CYP and UGT inhibitors and inducers

Eltrombopag is metabolised through multiple pathways including CYP1A2, CYP2C8, UGT1A1, and UGT1A3. Medicinal products that inhibit or induce a single enzyme are unlikely to significantly affect plasma eltrombopag concentrations; whereas medicinal products that inhibit or induce multiple enzymes have the potential to increase (e.g. fluvoxamine) or decrease (e.g. rifampicin) eltrombopag concentrations.

6.2.2 Prohibited medication

[figure not shown]
Any ITP directed therapy as per investigator assessment, different from what is specified within treatment section of the protocol, should be excluded including, but not limited to, platelet transfusion, new ITP-treating medication, or splenectomy. Detailed explanation related to exception for use of rescue medication is described in [Section 6.2.3](#).

Use of the treatments detailed below are not allowed after screening.

Patients must abstain from using investigational or not use marketed drugs without a well-known safety profile and from using prohibited prescription or nonprescription drugs within 7 days or 5-half-lives (whichever is longer) prior to the first dose of study treatment and until completion of follow-up procedures unless, in the opinion of the Investigator and Sponsor, the medication will not interfere with the study (see Exclusion Criteria-[Section 5.2](#)).

Patients must abstain from taking herbal supplements within 7 days (or 14 days if the drug is a potential enzyme inducer) or 5-half-lives (whichever is longer) prior to the first dose of study treatment until completion of the 30-day follow-up visit, unless the Investigator and Sponsor agree that the medication will not interfere with the study treatment.

Drugs that affect platelet function (including but not limited to, aspirin, clopidogrel and/or non-steroidal anti-inflammatory drugs [NSAIDS]) should not be taken during the study unless there

is a very clear indication and the Investigator documents the rationale. [REDACTED]

Any other TPO-R agonists are prohibited during this study (e.g., romiplostim).

6.2.3 Rescue therapy

Any ITP-directed medication or therapy, other than eltrombopag, given during the trial with the aim to increase platelet count for the patients who have clinically significant bleeding will be considered a rescue therapy and must be recorded on the appropriate CRF page. A patient who receives rescue medication or therapy will not be considered in having achieved sustained remission for the primary endpoint, unless the patient uses steroids ± IVIG as described below in the first 14 days of start of eltrombopag.

Steroids ± IVIG use as rescue medication:

In case of clinical necessities because of very low platelet count ($< 10 \times 10^9/L$) and/or significant bleeding, treatment with steroids ± IVIG and platelet transfusion is permitted together with eltrombopag for the first 14 days, calculated from the first dose day of eltrombopag.

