Patients who successfully taper off, i.e. discontinue eltrombopag and maintain platelet count $\geq 30 \times 10^9/L$ in the absence of bleeding or use of any rescue therapy will be followed up through the duration of the trial (to month 12). In case of relapse, patients will be offered a new course of eltrombopag treatment within this timeframe, starting at a dose of 50 mg.

Patients with bleeding, or perceived risk of serious bleeding, will be allowed to receive rescue therapy as per physician decision, irrespective of platelet counts.

A schematic depicting an example of a patient with sustained remission is provided in [Figure 3-2](#). Individual patient study experience will vary dependent on time to response and duration of eltrombopag tapering.

Figure 3-2 Example of a patient with sustained remission by Month 12

4 Rationale

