12.4.2 Statistical model, hypothesis, and method of analysis

The number (%) of patients with sustained remission (R) by month 12 will be summarized together with 95% confidence interval (CI) using the Clopper-Pearson method.

A binomial test for one proportion, $H_0: P=0.15$ vs. $H_1: P>0.15$ will be performed to test if the proportion of remission patients is greater than 15%.

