12.8 Sample size calculation

12.8.1 Primary endpoint

Based on medical experts' advice, it is postulated that approximately 15% of patients who do not respond or relapse after a first round of steroid therapy would have sustained remission by

12 months if on steroid recycling. In this study, at least a 10% higher sustained remission rate is expected by month 12, i.e., a sustained remission rate of at least 25% by 12 months is expected in patients who will receive eltrombopag after failing first-line steroids.

The sample size calculation is based on an exact binomial test for single proportion using a target alpha level of 0.05 and power of 80% to compare the null hypothesis $H_0: P=0.15$ against the alternative hypothesis $H_1: P>0.15$, where P is proportion of patients with sustained remission by Month 12.

A sample size of 101 gives at least 80% power if the true sustained remission rate with eltrombopag is 25% or more with an actual significance level of 0.043. The null hypothesis will be rejected if the number of patients with sustained remission is 22 or more.

Table 12-1 shows the sample size, cut-off, actual alpha, beta and power for different sustained remission rates. PASS 11 (version 11.0.10) is used for the sample size calculation.

Table 12-1 Numeric results for testing $H_0: P = P_0$ versus $H_1: P > P_0$ using exact binomial test statistic

Proportion given H_0 (P_0)	Proportion given H_1 (P_1)	Sample size (N)	Cut-off (Reject H_0 if $R \geq$ This)	Actual Alpha	Actual Beta	Actual Power
0.150	0.250	101	22	0.043	0.196	0.804
0.150	0.300	48	12	0.048	0.181	0.819
0.150	0.350	28	8	0.049	0.182	0.818
0.150	0.400	22	7	0.037	0.158	0.842
0.200	0.300	116	31	0.049	0.193	0.807
0.200	0.350	56	17	0.043	0.194	0.806
0.200	0.400	35	12	0.034	0.195	0.805

At the end of the study, for decision-making purposes, the cut-off will be determined based on the final sample size and the target alpha and beta.

13 Ethical considerations and administrative procedures

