2.4.2 Rescue therapy

Any ITP-directed medication or therapy, other than eltrombopag, given during the trial with the aim to increase platelet count for the patients who have clinically significant bleeding will be considered a rescue therapy and must be recorded on the appropriate CRF page (Form: Concomitant Medication, the category value at the form: Rescue medication). A patient who receives rescue medication or therapy between Step 2 and Step 3 will not be eligible for Step 3. A patient who receives rescue medication or therapy between Step 3 and Step 4 will not be eligible for Step 4. A patient who receives rescue medication or therapy will not be considered in having achieved sustained response off treatment for the primary endpoint, unless the patient uses steroids ± IVIG as described below in the first 14 days of start of eltrombopag.

Steroids ± IVIG use as rescue medication:

In case of clinical need such as very low platelet count (<10×10⁹/L) and/or significant bleeding, treatment with steroids ± IVIG and platelet transfusion is permitted together with eltrombopag for the first 14 days, calculated from the first dose day of eltrombopag. Any rescue therapy started before Day 14 may be used after Day 14 if the dose is considered low dose as per protocol definition and is being tapered down (i.e., successively lower doses after day 14).

Rescue medication will be taken from the SDTM cm.sas7bdat dataset where cmcat='RESCUE MED' for rescue therapy and exported as an EXCEL file. The clinical team will review the records captured in an Excel spreadsheet. Medications which were not considered as rescue therapy were flagged as 'Y' for the column 'NOT_RESCUE'. Per protocol, medications prior to Day 14 are not considered as rescue medication in the efficacy derivations and will be programmatically excluded. Medications that started prior to Day 14 and were still being tapered after Day 14 will also be programmatically excluded from efficacy derivations.

Once the database has locked the data will be rechecked again for any changes or new data that needs flagging.

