The spreadsheet will contain patient level data with patient number (USUBJID), sequence number (CMSEQ), reported drug name (CMTRT), standardized medication name (CMDECOD), category for medication (CMCAT), indication (CMINDC), dose per administration (CMDOSE), dose units (CMDOSU), dosing frequency per interval (CMDOSFRQ), start date/time of medication (CMSTDTC), end date/time of medication (CMENDTC), indication 1(CMINDC1), indication 2 (CMINDC2), reported name of drug trade name (CMTRDNAM), not rescue medication flag (NOT_RESCUE).

The spreadsheet will be imported into the programming environment (GPS) and merged with the patient data for the analysis. The EXCEL document will be stored in CREDI in the study folder ETB115J2411/Administrative Files (study level)/RAP or RAMP Meeting and in GPS in the study folder: CETB115J2411\csr_1\util.

Platelet transfusions will be taken from the ADCM and ADPR datasets. The variables category for medication (CMCAT), standardized medication name (CMDECOD), reported name of drug, medication, or therapy (CMTRT) from the ADCM will be used for the looking for platelets transfusions. The CMCAT values should be equal to 'RESCUE MED', and CMDECOD and/or CMTRT should contain the text 'PLATELET'. The variables contained reported names of procedure (PRTRT) and standardized procedure name (PRDECOD) from ADPR will be used for the looking for platelets transfusions. The PRDECOD and/or PRTRT should contain the text 'PLATELET'.

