2.7.1 Secondary endpoints

2.7.2 Efficacy endpoint(s)

1. To assess the **duration of sustained response off treatment** after treatment discontinuation
 - 1a) Summary statistics for the duration of sustained response off treatment (weeks) counted from last dose of eltrombopag to month 12 for patients with sustained response off treatment

(SRoT_M12 patients) will be provided. Mean, SD, median, maximum, minimum, 25th percentile and 75th percentile will be provided.

1b) Kaplan-Maier analysis and corresponding plot for the duration of sustained response off treatment for all patients meeting the primary endpoint (SRoT_M12 patients) (weeks) will be provided and is counted from last dose of eltrombopag to relapse. The SRoT_M12 patients who do not relapse/ restart eltrombopag treatment until month 24 will be censored.

- Event: relapse after achieving SRoT_M12 (platelets <30 Gi/L, bleeding event, rescue therapy/platelet transfusion, or restarted eltrombopag treatment)
- Censoring rules: Patients with SRoT_M12 who enter follow-up and do not relapse by cut-off date/Month 24 will be censored at the earliest of discontinuation date/death date/M24 platelet assessment date/cutoff date. SRoT_M12 patients who did not enter or do not yet have platelet assessments in follow-up phase are censored at their M12 platelet assessment date.

1c) Kaplan-Maier analysis and corresponding plot for the duration of sustained response off treatment for all patients who achieved Step 3 (S3 patients) (weeks) will be provided and is counted from their last dose of eltrombopag on or before this last S3 to relapse.

The S3 patients who do not relapse/ restart eltrombopag treatment until month 24 will be censored.

The event and censoring rules are as in 1b) above.

It is noted that the SRoT_M12 patients are a subset of patients in the group of patients who achieved Step 3 (S3 patients).

Duration of SRoT (weeks) for the tapered patients who achieved step 3 will be summarized by SRoT_M12 status.

2. To assess the proportion of patients maintaining a sustained response off treatment after treatment discontinuation until month 24. Number (%) of patients who are in sustained response off treatment at months 15, 18, 21, and 24 will be provided.
3. To assess the ability of eltrombopag to induce **early response by month 1**

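### Whether non-transfusion ITP therapy given after Day 14 without clinically significant bleeding counts as rescue depends on the site's CRF category, and splenectomy is never searched for

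*Protocol*

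**What the plan says.** **Definition.** Protocol Section 6.2.3 and SAP Section 2.4.2 both state that ITP-directed treatment other than eltrombopag "with the aim to increase platelet count for the patients who have clinically significant bleeding will be considered a rescue therapy". Receiving rescue means non-response, apart from permitted use in the first 14 days. SAP Section 2.4.2 extends that allowance to treatment begun before Day 14 and being tapered.

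**Wider use of the word.** Protocol Section 3 (repeated in SAP Section 1.1) says: "Patients with bleeding, or perceived risk of serious bleeding, will be allowed to receive rescue therapy as per physician decision, irrespective of platelet counts". The second part of Protocol Section 6.2.3 also accepts a very low count alone as a reason for rescue in the first 14 days.

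**Other ITP therapy.** Protocol Section 6.2.2 excludes treatments such as "platelet transfusion, new ITP-treating medication, or splenectomy". Section 9.1.1 makes prohibited treatment a reason to stop study treatment, and adds that stopping treatment is not withdrawal from the study. Neither section says how the endpoint is then scored.

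**Data source.** SAP Section 2.4.2: "Rescue medication will be taken from the SDTM cm.sas7bdat dataset where cmcat='RESCUE MED' for rescue therapy". The clinical team then flags listed records that it does not regard as rescue. Transfusions are sought in the medication data and also in the procedures data, with the rule "The PRDECOD and/or PRTRT should contain the text 'PLATELET".

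**Months 12 to 24.** A patient given anything other than eltrombopag leaves the study (Protocol Sections 6.1.3 and 9.3). In SAP Section 2.7.2, items 1b and 1c, the events are a count below 30 × 10⁹/L, bleeding, rescue or platelet transfusion, and restart of eltrombopag. Patients without an event who entered follow-up are "censored at the earliest of discontinuation date/death date/M24 platelet assessment date/cutoff date".

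**The concern.** The primary endpoint already fails a patient with a bleeding AE. The no-rescue condition therefore adds something mainly when treatment is given without bleeding, and that is the case the written definition leaves out. Platelet-raising treatment in the drug-free period can itself hold counts at or above 30 × 10⁹/L, so a patient maintained on steroids or IVIG could be scored as responding off treatment.

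The error runs one way, towards too many responders. The trial is single-arm and tested against a fixed 15%, so no control group carries the same error to offset it. Responder status at month 12 also defines the groups in which selected final-CSR outputs are shown (SAP Section 2.2.1).

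In follow-up, starting another ITP therapy signals loss of treatment-free response. Censoring it as uninformative would lengthen the Kaplan-Meier durations in 1b and 1c.

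**Working it through.** **Step 1. What happens, under the text, after Day 14 and up to month 12.**

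| Event | Where the rule is | Fails the patient? |
|---|---|---|
| Platelet transfusion | SAP 2.5.2, third case; procedures search needs no rescue category | Yes, bleeding or not |
| Medication the site categorised as rescue | SAP 2.4.2, 2.5.2 | Yes, unless the review or the Day-14 rules remove it; the program makes no bleeding check |
| Steroid, IVIG, anti-D, other TPO-RA or immunosuppressant, no bleeding, entered as ordinary concomitant medication | None | No |
| Splenectomy | Procedures searched only for the platelet text | No |
| Scheduled count below 30 × 10⁹/L | SAP 2.5.1 | Yes |
| Unscheduled count below 30 × 10⁹/L | SAP 2.5.1 uses scheduled counts only in the first 12 months | No |
| Bleeding AE | SAP 2.5.1 | Yes |
| Leaving the study before month 12 | Protocol 12.4.3, SAP 2.5.3 | Yes |

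The third and fourth rows are the gap. No described step adds a record from outside the rescue category. The criterion for the removal flag is not given, so a reviewer applying the written definition could also remove a non-bleeding record that a site had categorised as rescue. The prohibition does not close the gap, because a patient who has already tapered off has no study treatment to stop. The sixth row weakens the platelet backstop: an unscheduled low count followed by treatment can leave every scheduled count at or above 30 × 10⁹/L.

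**Step 2. Months 12 to 24.** All counts, scheduled or not, are used. A patient who starts another ITP therapy leaves the study, and is censored at discontinuation unless one of the listed 1b/1c events has been captured.

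**Step 3. Sensitivity of the decision rule.** Inputs: the binomial test "will be performed to test if the proportion of remission patients is greater than 15" per cent (Protocol 12.4.2); the design "using a target alpha level of 0.05 and power of 80" per cent (Protocol 12.8.1); n = 105, cut-off 23, actual alpha 0.037, power 0.800 at a true rate of 25% (SAP 3.1.2).

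Formula: P(X ≥ r) = Σ from k = r to n of C(n,k) pᵏ(1−p)ⁿ⁻ᵏ.

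The plan's own figures first:
- n = 101, r = 22: alpha 0.0433, power 0.8042 (stated 0.043 and 0.804).
- n = 105, r = 23: alpha 0.0373, power 0.7995 (stated 0.037 and 0.800).

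Both reproduce to the precision given.

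Now suppose that the true rate is 15% and m patients are wrongly added to the responders. H0 is rejected when X + m ≥ 23, that is X ≥ 23 − m:
- m = 0: P(X ≥ 23) = 0.0373
- m = 1: P(X ≥ 22) = 0.0626
- m = 2: P(X ≥ 21) = 0.1001
- m = 3: P(X ≥ 20) = 0.1527

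Adding 1, 2 or 3 percentage points to the rate instead (about 1, 2 or 3 of 105) gives P(X ≥ 23) = 0.0688, 0.1155 or 0.1789.

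At the boundary, 23 responders give p = 0.037 and 22 give p = 0.063. With 26 responders (p = 0.006), removing three leaves 23 and H0 is still rejected.

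**The case against.** The best defence is that the plan as a whole treats rescue as separate from bleeding. Protocol Section 3 calls treatment for perceived risk rescue, and SAP Section 1.1 lists rescue alongside bleeding in its definition of relapse. A site reading these would probably choose the rescue category, and the program would then count the record.

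Such treatment should also be uncommon. Other ITP therapy is prohibited except as rescue, and relapse after stopping is to be met with eltrombopag. A misclassified patient must complete the taper, receive non-transfusion therapy without bleeding, have it categorised elsewhere and show no scheduled count below 30 × 10⁹/L at roughly two-weekly visits. Medications and procedures are all recorded and listed, deviations are listed, and primary-variable data are fully source-verified.

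In follow-up, any count below 30 × 10⁹/L is an event, and a patient leaving between defined visits should complete the end-of-follow-up visit, which includes hematology.

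Much of this stands. It makes the gap narrow and its frequency probably low. It does not supply a rule: listing and verifying a record do not make it an endpoint failure, and the two meanings of rescue leave the choice of category to the site.

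**Conclusion.** The point holds for non-transfusion ITP-directed therapy given after Day 14 without clinically significant bleeding. It lies outside the written rescue definition. For medication, its effect on the primary endpoint depends on the site's CRF category; splenectomy has no effect at all, unless another criterion fails the patient. In months 12 to 24 such therapy is censored in 1b and 1c when no listed event is captured.

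A reader might infer more, and the documents do not support it:
- That all ITP treatment without bleeding is ignored. Transfusions after Day 14 already bar response, and records categorised as rescue are not tested for bleeding.
- That such treatment is expected off drug. Outside rescue it is prohibited.
- That the type I error is in fact 6.3% to 15.3%. Those figures assume one to three false responders at a true rate of 15%. The documents give no number, and the same arithmetic would apply to any misclassification. It shows only that one patient can decide a result at the cut-off.

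**What to change.** For scoring only, with no change to care:

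1. Reconcile the wording of rescue in Protocol Section 3 and SAP Section 1.1 with Protocol Section 6.2.3 and SAP Section 2.4.2.
2. In SAP Sections 2.4.2, 2.5.2 and 2.7.2 (1b and 1c), count any ITP-directed therapy other than eltrombopag that is newly started or increased after Day 14 as failure or relapse at its start date, with or without bleeding. Keep the SAP's allowance for steroids begun before Day 14 and being tapered.
3. Identify such therapy from all concomitant-medication records, by ATC class or standardized name together with indication, and from all procedure records, including splenectomy.
4. The primary CSR is final and the trial is open-label, so do not replace the primary result. Report the re-derived month-12 proportion in the final CSR as a labelled sensitivity analysis, and correct the 1b/1c event rule before the final lock.

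The data are already collected and coded, so the cost is SAP wording, programming and a clinical review of a longer list. Sample size, cut-off and alpha stay as they are. The responder proportion and the estimated duration may fall slightly.

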6.3 Patient numbering, treatment assignment, randomization

6.3.1 Patient numbering

Each patient is identified in the study by a Patient Number (Patient No.), that is assigned when the patient is first screened and is retained as the primary identifier for the patient throughout his/her entire participation in the trial. The Patient No. consists of the Center Number (Center No.) (as assigned by Novartis to the investigative site) with a sequential patient number suffixed to it, so that each patient is numbered uniquely across the entire database. Upon signing the informed consent form, the patient is assigned to the next sequential Patient No. available.

The investigator or designated staff will contact the IRT and provide the requested identifying information for the patient to register them into the IRT. Once assigned, the patient ID must not be reused for any other patient.

If the patient is re-screened, a new unique number will be assigned to the rescreened patient and the original assigned number will be captured in the rescreening page. If the patient fails to start treatment for any reason, the reason will be entered into the Disposition page. IRT must be notified within 2 days that the patient was not enrolled in the study.

